- 1) To determine the correlation between glucose readings using the ANICGM an AccuChek Inform II blood glucose meter in patients with type 2 diabetes at baseline and after ingestion of a glucose load throughout a complete glucose excursion

-Rationale: a continuous glucose monitor needs to capture rapid postprandial glucose increases and returns to baseline levels

- 2) To ascertain if the ANICGM calibration is maintained up to 14 days

-Rationale: the ANICGM is being developed for use for multiple days

Note: The results from the ANICGM meter will not be used to guide any aspect of the patient's treatment course.

Description of the technology

The ANICGM uses a weak electromagnetic field generated by its wrist band sensor to look into the body to produce a spectrum that provides a measurement of blood glucose present in the wrist area of the body. The core sensing technology used is dielectric spectroscopy, and has been shown capable of measuring blood glucose, non-invasively, in a laboratory environment (1-3). The system uses proprietary and patented dielectric materials and signal processing to enhance performance in both selectivity and sensitivity for blood glucose measurement.

Much like how a MRI uses a strong magnetic field and its interaction with the body to create a picture of what is inside, the ANICGM uses a safe weak low frequency radiofrequency field to take a picture of a person's chemical spectrum, some of it specific only to blood glucose.

The device sends and receives back signals from the wrist area that are used to generate a dielectric spectrum once every 6 seconds. This spectral data is stored on the device, and then downloaded wirelessly or through USB port to an Alertgy laptop. The POC BG using the Accuchek Inform II will be used to provide calibration values for the ANICGM every 5 minutes in mg/dL, during the calibration process. The POC BG levels will be entered into the Alertgy laptop and a proprietary calibration program will be used to analyze the spectral data collected and will generate a calibration algorithm. The Alertgy support team will provide the ANICGM data to compare to the POC BG data they collected concurrently during the tests.

Description of the device

The present band is about 5 inches long made out of inert plastic material. It is applied to the wrist area and adjusted to a snug fit. All of the materials that make contact with the body are inert. A photo is included below.

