(This is the current model. An improved version may be available at the time of the study).

Cleveland Clinic staff will be trained by a written instruction manual in the application and use of the device by Alertgy staff on site. As the device is automated and noninvasive, it is anticipated that the training period will take no longer than two hours maximum.

Preliminary data

[figure not shown]
Data from Alertgy in the graph below shows testing of 8 subjects in their lab showing correlation between the ANICGM (y-axis) and the Abbott Freestyle Neo glucometer (x-axis).

Of the 8 subjects, 3 had type 2 diabetes (2 of whom are on insulin), 2 had prediabetes, and 3 did not have prediabetes or diabetes.

Pearson's correlation was used, $R^2= 0.993$.

Clarke Error Grids

- 8 Subjects
- Single Calibration Method

Inclusion Criteria

Type 2 diabetes on diet or on pharmacologic treatment for diabetes

Hemoglobin A1c (HbA1c) 7.5-10.0%

- below 7.5%, there may not be a demonstrable blood glucose spike
- above 10.0%, subjects are more likely to be symptomatic from hyperglycemia and require treatment during the study

Age 18-75 years old

Exclusion Criteria

Patients taking prandial insulin

Fasting blood glucose by fingerstick <70 mg/dL or >250 mg/dL. Hypoglycemia <70 mg/dL will be treated according to clinic protocol.

Pregnancy

ESRD

Decompensated or acute heart failure

Medications that might cause false readings with glucose meters: acetaminophen, ascorbic acid, dopamine, maltodextrin, mannitol

Conditions that limit the ANICGM such as lesions on the forearms

Other conditions that the investigators deem will affect the conduct of the study

Protocol

There are 3 study visits: Visit 1, Visit 2 (3-14 days after Visit 1) and Visit 3 (5-14 days after Visit 1)

Alertgy personnel will undergo the onboarding process utilized by CCF Innovations called Silkroad/Red Carpet. Personnel undergoing this process complete 8 Comet modules (code of conduct, corporate complaints, HIPPA overview and HIPPA & IS Security Awareness, Emergency Management, Environment of Care, Patient Safety and Energy Savings).

Study Calendar

	Visit 1	Visit 2	Visit 3
	Day 1	3-14 days	5-14 days
Informed Consent	X		
Inclusion/Exclusion	X		
Medical History	X		
Urine Pregnancy Test *	X	X	X
Vitals	X	X	X
Comorbidities	X		
Adverse Events Assessment	X	X	X
Medication Review	X	X	X
Ingest GlucoCrush	X	X	X
Glucose Collection (Fingersticks)	X	X	X

*Women with childbearing potential

For all study visits

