The timing of the fingerstick blood glucose checks outlined below are approximate, as there might be occasions where the fingerstick might not be performed at the exact minute specified (for example, patient needing to go to restroom, issues with the Accuchek Inform II glucose meter, etc). Every effort will be made to do the fingerstick at the specified time.

Subject fasts overnight, then proceeds to Cleveland Clinic Main Campus Adult Endocrinology clinic at F20.

Vital signs will be taken.

Women with childbearing potential will have a urine pregnancy test before each study.

Patients will be asked to bring diabetes medications (and related devices) if requiring injections to F20.

If a subject is on basal insulin, the subject will take the basal insulin as close to the usual time as possible.

A baseline fingerstick blood glucose (BG) will be taken using the clinic's Accuchek Inform II glucose meter (time -60 min); this is needed to determine eligibility.

If BG 70-150 mg/dL subject will hold their morning medications or delay taking their diabetes medication until after the procedure (except for basal insulin as above) upon instructions of the investigator.

If BG 151-250 mg/dL, subject will take their diabetes medication at the usual time to prevent symptomatic hyperglycemia.

The ANICGM will be placed on the wrist. Measurements from the ANICGM start immediately. There will be a period of 20 minutes to allow the ANICGM to stabilize to body temperature.

Fingerstick BG will be repeated at time -30 min, -15 min, and 0 min for baseline validation.

At time 0 min, subjects ingest 75 g oral glucose drink (GlucoCrush)

For Visit 1:

Since the ANICGM is using new technology that depends on calculating the slope of the fingerstick glucose change to individualize the calibrations, it is crucial to have frequent fingersticks during Visit 1 for the first hour after the glucose challenge (GlucoCrush).

After the GlucoCrush, fingerstick BG will be done every 5 minutes for 2 hours.

Other continuous glucose devices have done monitoring as frequently as this (see attachment, figure 7, from Choi H, Naylor J, Luzio S, Beutler J, Birchall J, Martin C, Porch A. Design and *In Vitro* Interference Test of Microwave Noninvasive Blood Glucose Monitoring Sensor. IEEE Trans Microw Theory Tech. 2015 Oct 1;63(10 Pt 1):3016-3025)

For Visit 2 and Visit 3:

Fingerstick BG will be taken every 15 minutes for 2 hours after ingestion of GlucoCrush

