Other continuous glucose devices have done monitoring as frequently as this (see attachment, figure 8, from Choi H, Naylor J, Luzio S, Beutler J, Birchall J, Martin C, Porch A. Design and *In Vitro* Interference Test of Microwave Noninvasive Blood Glucose Monitoring Sensor. IEEE Trans Microw Theory Tech. 2015 Oct 1;63(10 Pt 1):3016-3025)

For all study visits

Wrist device is removed after each study visit. In-between patients, either same or different day, the device will be cleaned by using Super Sani Cloth wipes, which are the disinfectants we have in the endocrine clinic (active ingredients: dimethyl ethylbenzyl ammonium chloride, isopropyl alcohol)

[figure not shown]

Fig. 7. OGTT I. The sensor response (here the change in bandwidth) is compared with blood glucose levels measured using a “blood-strip” glucometer (Bayer CONTOUR).

[figure not shown]

Fig. 8. OGTT II. Sensor data (change in bandwidth) are measured over a continuous 12-h period involving three food ingestions, and are compared with data from a continuous glucose meter (Medtronic Guardian CGM) and blood-strip glucometer (Bayer CONTOUR), after [27].

Sample Size

It is expected that 10-15 subjects will be enrolled, and that there will be up to 24 paired measures on Visit 1 (every 5 minutes for 2 hours), and 8 paired measures (every 15 minutes for 2 hours) each of the follow-up days. If no errors on the Clarke error grid are observed (as in the preliminary data), the error rate based on the “rule of three”, will be constrained to be no more than 0.5% overall (based on 600 total measures), and no greater than 5% within subject (Jovanovic and

Levy, 1997). Confidence limits for the agreement will depend on the within and between subject variability measures, so formal power calculations on this measure of agreement is not possible.

Statistical analysis

Agreement between glucose measures between systems will be evaluated graphically using Bland-Altman plots, and Clarke error grids. Error rates from the Clarke error grid will be calculated, and 95% confidence limits will be calculated overall, by subject and by day within subject. Similarly, limits of agreement from the Bland-Altman plots will be adjusted to account for repeated measures, as described by Bland and Altman (2007). Analysis will be performed using SAS software (version 9.4; Cary, NC).

Possible adverse effects

The materials for the wrist band are inert and the potential for allergy is low.

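### Every visit repeats the same timed glucose curve that the device is calibrated on, and the analysis has no reference predictor to show how much Visit 2–3 agreement replaying that curve would give

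*Combined protocol and SAP*

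**What the plan says.** Under Protocol, For all study visits, one sequence applies to Visits 1, 2 and 3.

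- Start: "Subject fasts overnight, then proceeds to Cleveland Clinic Main Campus Adult Endocrinology clinic at F20".
- Band: placed after the −60 min fingerstick; "There will be a period of 20 minutes to allow the ANICGM to stabilize to body temperature". It is taken off after each visit, so it is re-applied each time.
- Baseline: "Fingerstick BG will be repeated at time -30 min, -15 min, and 0 min for baseline validation".
- Load: "At time 0 min, subjects ingest 75 g oral glucose drink (GlucoCrush"). The Study Calendar row "Ingest GlucoCrush" is marked at all three visits.

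Only the later sampling differs. Visit 1 has a fingerstick every 5 minutes for 2 hours. For Visits 2 and 3, "Fingerstick BG will be taken every 15 minutes for 2 hours after ingestion of GlucoCrush".

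Calibration is individual and depends on the slope of the Visit 1 fingerstick change (For Visit 1). Under Description of the technology, "a proprietary calibration program will be used to analyze the spectral data collected and will generate a calibration algorithm".

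Under Statistical analysis, "Agreement between glucose measures between systems will be evaluated graphically using Bland-Altman plots, and Clarke error grids". Clarke error rates are given overall, by subject and by day within subject, and the limits of agreement allow for repeated measures. No reference predictor, time-only model or performance threshold is named.

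**The concern.** The band is re-applied before each visit's load, so time on the wrist restarts and runs nearly in step with time since the load. A signal that changes with time on the wrist could be fitted to a subject's Visit 1 curve. It could then yield a similar curve at Visits 2 and 3, where the reference glucose is also likely to follow a similar course. Agreement there mixes two sources: sensing glucose, and reproducing the subject's usual response. The plan reports the sum and has nothing to set it against.

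Visits 2–3 carry Aim 2 (calibration held up to 14 days), and they are the only data outside the calibration visit that bear on Aim 1. Good agreement there would naturally be read as proof that the sensor works and stays calibrated. The section on the relationship between the manufacturer and the clinic also ties a financial decision to that conclusion.

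**Working it through.** **The plan's own figure.** Sample Size takes zero Clarke errors as its favourable case. Pairs per subject: 24 + 8 + 8 = 40. With 15 subjects, 15 × 40 = 600 and 3/600 = 0.5%, which reproduces. (The 5% within-subject bound does not: 3/40 = 7.5%. That is a separate matter.) Of the 600 pairs, 15 × 24 = 360 come from the calibration visit and 15 × 16 = 240 from Visits 2–3.

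**Is replay definable from the planned data?** Yes. The Visit 2–3 minutes 15, 30, …, 120 all lie on the Visit 1 5-minute grid, and −30, −15 and 0 min occur at every visit. That gives 8 + 3 = 11 matched minutes per visit.

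**How well would replay score?** The predictor is the same subject's Visit 1 fingerstick at the same minute, scored against the Visit 2–3 fingerstick at the 8 post-load points. Zone A means within 20% of the reference, or both at or below 70 mg/dL. The documents give no day-to-day variation, so all inputs below are assumptions, with 5% meter error throughout.

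*Set 1.* Fasting 90–230 mg/dL, rise 80–180 mg/dL, peak at 60–100 min.

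| Fasting SD (mg/dL) / rise CV | Zone A, Visit 1 equal to the usual curve | Zone A, all visits vary |
|---|---|---|
| 10 / 10% | 97% | about 93% |
| 20 / 20% | 86% | about 75% |
| 30 / 35% | 70% | about 55% |

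Letting the time to peak vary as well lowers these figures slightly.

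*Set 2.* Fasting mean 160 (SD 30) mg/dL, rise 130 (SD 30) mg/dL, time to peak T of 80 (SD 12) min. Curve: fasting + rise × (t/T)² × exp(2(1 − t/T)). All visits vary; 15 subjects, 240 pairs.

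| Day-to-day log-SD: fasting / rise / peak time | Zone A | Zones A+B | Chance of zero errors in 240 pairs |
|---|---|---|---|
| 0.05 / 0.10 / 0.05 | 95% | >99.9% | 95% |
| 0.10 / 0.15 / 0.10 | 83% | 99.5% | 50% |
| 0.15 / 0.25 / 0.15 | 66% | 96.7% | 4% |
| 0.20 / 0.35 / 0.20 | 53% | 91.8% | 0.1% |
| 0.30 / 0.50 / 0.25 | 40% | 82.9% | 0% |

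In the first two rows, a predictor with no current glucose information would show zero errors at Visits 2–3 in about 50–95% of studies. In the last three it would rarely or never do so.

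**Can the existing data separate the two?** Let D be the device reading and F the fingerstick, for subject i at minute t. Fit

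F3(i,t) − F2(i,t) = α + β [D3(i,t) − D2(i,t)] + error, clustered by subject.

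A replay device gives the same underlying value at both visits, so D3 − D2 is noise unrelated to F3 − F2 and β = 0. A sensor gives β > 0. In simulation with 15 subjects, replay was declared a signal in about 3–4% of studies. A true sensor with 10–15% error was detected in about 60–85% under small variation and in 97% or more under larger variation.

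Regressing F2 on D2 with adjustment for the Visit 1 fingerstick is less safe. That fingerstick carries meter error, so a replay device holding a smoother version of the Visit 1 curve can still add to the prediction and pass.

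**The case against.** **The confounding is not complete.** Fasting glucose can differ between visits, and whether morning medication is taken depends on the day's fasting value. Timings are approximate, and the exact minute of application is not fixed. Error rates by day could also expose a replay that fails. This stands. A reader might infer that Visits 2–3 cannot separate sensing from replay; the documents do not support that. The separating information exists, and the plan does not use it.

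**Perfect replay is a best case for an artefact.** It reuses the actual fingersticks. Simple warming or drift would have to follow a rise and fall and keep its level after re-application, and 20 minutes are allowed for temperature to settle. For the Set 2 curve, the correlation of time with glucose within 2 hours is 0.67 to 0.95 if the peak falls at 75–110 min, but only −0.32 to 0.18 at 50–60 min. This stands too, so the replay scores are upper bounds.

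**A benchmark could be misused.** Requiring the device to beat replay would fail real sensors. One with 10% error beat replay on mean absolute relative difference in only about 1–3% of 15-subject studies under small variation. This is right, and it rules out such a gate.

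None of this supplies the missing comparison.

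**Conclusion.** The point holds as a gap in the analysis. The repeated sequence, the per-subject calibration on Visit 1 and the absence of any comparator or threshold are all in the document. Agreement at Visits 2–3, reported alone, cannot be apportioned between sensing and reproduction of the usual curve.

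The size rests wholly on assumed day-to-day variation: roughly 92–97% zone A for replay if small, 73–86% if moderate and 54–70% if large, lower still beyond that, with more readings outside zones A+B as variation grows.

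A reader might go further and infer that the device has no glucose signal, or that both aims fail. Nothing in the document shows that the device replays anything. The point concerns Visits 2–3: mainly Aim 2, and Aim 1 only so far as it draws on those visits.

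**What to change.** Add to Statistical analysis, before data are seen and for Visits 2 and 3 only:

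1. **Reference predictor.** Use the same subject's Visit 1 fingerstick at the same protocol minute (−30, −15, 0 and each 15-minute point). Report its Bland-Altman limits, Clarke zone percentages and mean absolute relative difference beside the device's, with subject-clustered confidence limits for the difference. Treat this as descriptive; do not make beating it a condition for concluding that the device measures glucose.
2. **Test of signal.** Regress the fingerstick's Visit 3 minus Visit 2 difference on the device's difference at the same minute, clustered by subject. Prefer this to adjustment for the single Visit 1 fingerstick.
3. **Reading.** State that a null result means not distinguishable from replay, not that the device does not measure glucose.

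The cost is a short piece of SAS code on data already collected, with no extra visit or fingerstick. The device may look less impressive beside the reference. The test uses only subjects with both later visits, and its power is limited if subjects' curves are very stable.
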